SAEs	- Employee injury requiring hospitalization during study events	We will monitor these directly at study events that research staff are present at, and ask employee leadership/staff/peers to report them if we are not in attendance.	ASAP, but no later than 3 working days, regardless of whether SAE is study-related	ASAP, but no later than 3 working days	ASAP, but no later than 3 working days
Other AEs	- Employment discipline for improper handling of participant	We will document these events, when we learn of them, per peer supervisors/CBO	Annually. Note that documentation of these events	Tri-Annually	Tri-Annually

	
 - Employee distress related to managing a participant positive for COVID-19 - Staff breach of confidentiality 	leadership and peer to self-report.	must also indicate whether they are thought to be study related and why or why not.		
Unexpected AEs	An AE whose nature, severity, or frequency has not previously been identified. Also includes any adverse event that results in a participant's withdrawal from the study; or is due to a deviation in the research protocol	We will ask all study staff to raise concerns that they have directly via email.	ASAP, but no later than 5 working days.	Immediately if related to study. Tri-Annually if not related to study.	Immediately if related to study. Tri-Annually if not related to study.
Unanticipated Problems that are Not AEs	Incidents or outcomes that occur during human subjects research that are not AEs, but that involve social or economic harm (instead of physical or psychological harm), or are problems that place subjects or others at increased risk of harm, but where no harm occurs.	We will ask all study staff to raise concerns that they have directly in-person or via email.	ASAP, but no later than 5 working days. If MPIs deem the event likely to affect participants, it must be reported to the IRB immediately.	Immediately if related to study. Tri-Annually if not related to study.	ASAP, but no later than 3 working DAYS
Protocol Violations	Deviations from the IRB-approved study procedures, as outlined in the Protocol Summary Form that has received review and approval by	We will meet internally once a week to review study activities and, if we determine we have violated our protocol, we will record the incident	Within 2 weeks of staff becoming aware of the violation; no later	Annually	Annually- Should be included in the full data report

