	the IRB. A significant protocol deviation would be a deviation that increases the risk to participants or others, or decreases the potential benefits of the study, undermines the scientific integrity of the study, or occurs more than once	and remediate immediately.	than 5 days if the violation results in an unanticipated problem.		
IRB-or-PSMB determined suspension	Any suspension or termination of approval must be reported including a statement of the reason(s) for the action.	We will comply with IRB, DSMB, and NIMH procedures and guidance.	3 business days	3 business days	3 business days

Table 3.3b Method of Ascertainment of Serious and Adverse Events, and Unanticipated Problems for TESTING PARTICIPANTS (Sample 1)

Reportable Event	What they are in the study	Method of Ascertainment	Reporting Requirements		
			IRBs	PSMB	NIDA PO
Death	
 - Suicide event - Non-suicide death during study operations 
 - Death by overdose 	
Via peer supervisors, site coordinators and agency leadership self- report any deaths as soon as they learn of them.
 
Note: follow-up appointment status update
	ASAP, but no later than 3 working days	Immediately	ASAP, but no later than 3 working days
SAEs	
 - Suicide attempt following disclosure of suicidal ideation during assessment - Participant transport to 	Participants who endorse suicidal ideation and present as high-risk after emergency protocol is enacted may be referred to emergency services	ASAP, but no later than 5 working days, regardless of whether SAE is study-related.	ASAP, but no later than 3 working days	ASAP, but no later than 3 working days

	emergency services Non-lethal Overdose	by study staff if applicable. We will follow-up with participants who initially endorse suicidal ideation and are determined to be low-risk 3-7 days from their initial visit to assess suicidal risk. If participant self-reports suicide attempt we will document the SAE and report it as required, and link participant to mental health services.			

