Other AEs	- Distress related to a COVID-19 positive test - Remission (substance use) following recruitment - Coercion into participating by peer recruit - Breach of confidentiality	We will ask all study staff to raise concerns that they have directly in-person or via email and we will also ask about any potential problems during our check-in calls with CBO leadership and peer supervisors.	Annually. Note that documentation of these events must also indicate whether they are thought to be study related and why or why not.	Tri-Annually	Tri-Annually
Unexpected AEs	An AE whose nature, severity, or frequency has not previously been identified. Also includes any adverse event that results in a participant's withdrawal from the study; or is due to a deviation in the research protocol	We will ask all study staff to raise concerns that they have directly in-person or via email and we will also ask about any potential problems during our check-in calls with CBO leadership and peer supervisors.	ASAP, but no later than 5 working days.	Immediately if related to study. Tri-Annually if not related to study.	Immediately if related to study. Tri-Annually if not related to study.

Unanticipated Problems that are Not AEs	Incidents or outcomes that occur during human subjects research that are not AEs, but that involve social or economic harm (instead of physical or psychological harm), or are problems that place subjects or others at increased risk of harm, but where no harm occurs.	We will ask all study staff to raise concerns that they have directly in-person or via email and we will also ask about any potential problems during our check-in calls with CBO leadership and peer supervisors.	ASAP, but no later than 5 working days. If MPIs deem the event likely to affect participants, it must be reported to the IRB immediately.	Immediately if related to study. Tri-Annually if not related to study.	ASAP, but no later than 3 working days

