3.3.3.1. Protocols for preventing/mitigating specific risks. Participant distress will be managed by supervising clinical staff at either Argus or Alliance. Should additional assistance be required, supervising clinical personal within either agencies will contact the PI [name], a licensed clinical psychologist, who will provide further assistance. Risks associated with breaches of confidentiality and resulting retribution due to staff responses are a concern. Breaches of confidentiality are unlikely, given the PI's commitment to and experience in maintaining participant confidentiality. Breaches are not anticipated at NYSPI/CUMC offices, because as a research facility, standards for maintaining participant confidentiality have been rigorously maintained since we began research. Breaches might nonetheless occur. During the informed consent process, participants will be told of the confidentiality procedures that are in place, but will be informed that a breach is still possible, however rare, despite these procedures. Should a breach occur, four steps will be taken. First, the participant will be informed as to the nature of the breach, and its possible ramifications. Second, the PI will immediately notify the NIDA Project Officer and the IRB. Third, the PI will review existing confidentiality safeguards to determine why and how the breach occurred (outlined below). Fourth, the PI will halt data collection until such time that the IRB can review existing procedures as to their quality and completeness. The following steps are in place to guard against breaches of confidentiality and to protect confidentiality of research data:

- 1) Provisions in all protocols will be made to ensure that a) all participants review IRB approved consent (information) forms, b) all surveys are conducted on-line via secure login and data held on a secure server or conducted via pen/paper at the participants choice of location and pace , c) no personal identifying information is collected on data forms, d) all administrative data collected are stripped of identifying information, e) no public data files contain any HIPPA identifiers, f) participants understand the voluntary nature of study participation, g) all data collected are kept in a secured, locked area with access by only certified research staff, and h) all approvals and documentation from the IRB and other approval entities are easily accessible by the PIs and research coordinators.

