3.3.3.3 Protocol for reporting of adverse events. Events that are serious or unexpected must be recorded using the ethics committees' SAE/Unexpected Event forms and submitted to the New York State Psychiatric Institute (NYSPI) IRB within 5 working days from the time that research staff becomes aware of the SAE or AE (See Table). The PI must review the SAE form and sign and date the form; the PI will be responsible for informing the NYS Psychiatric Institute (Columbia University) IRB and the NIDA Program Officer.

Regular monitoring of the study will be undertaken by the PI and other research designated staff (e.g. PD) every three months to ensure that all study procedures are being adhered to, that record-keeping is accurate, and that adverse events are being identified and followed up. Below we summarize types of events and reporting requirements.

3.3.4 DSMB Project Review. While the PI ([name]) will have ultimate responsibility for reviewing conduct for the study and data emanating from it, including the reporting of any adverse events to the Institutional Review Boards of Columbia University/the New York State Psychiatric Institute (NYSPI), the Data Safety Monitoring Board as assembled by the CDCC through the RADx-UP consortium will meet to review this project at least once each year in addition to reviewing quarterly data safety reports prepared by the research. After the meeting, the DSMB members present written feedback to the research. This feedback will be shared with NIDA program officers, and with the respective IRBs.

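### A breach of confidentiality has two incompatible reporting clocks: immediate to the IRB and NIDA in section 3.3.3.1, but annual and tri-annual in Tables 3.3a and 3.3b

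*Combined protocol and SAP*

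**What the plan says.** **Text.** Section 3.3.3.1 accepts that breaches might occur and lists four steps for the PI. The participant is told. Then: "Second, the PI will immediately notify the NIDA Project Officer and the IRB". The safeguards are re-examined. Finally: "Fourth, the PI will halt data collection until such time that the IRB can review existing procedures as to their quality and completeness".

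**Tables.** Table 3.3b (testing participants) lists the event in the Other AEs row: "Coercion into participating by peer recruit - Breach of confidentiality". The IRB entry for that row is "Annually. Note that documentation of these events must also indicate whether they are thought to be study related and why or why not". The board (PSMB) and NIDA entries are tri-annual. Table 3.3a (staff) lists "Staff breach of confidentiality" in its own Other AEs row, with the same three clocks.

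**SAE clocks to the IRB.** Table 3.3a has "ASAP, but no later than 3 working days, regardless of whether SAE is study-related" and Table 3.3b has "ASAP, but no later than 5 working days, regardless of whether SAE is study-related". Section 3.3.3.3 wants serious or unexpected events submitted "within 5 working days from the time that research staff becomes aware of the SAE or AE".

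**The concern.** One named event carries two reporting times for the same two recipients, and the times differ by months. A person who looks up a breach in either table finds it by name, beside distress and other events reported periodically, with no pointer to the urgent procedure in 3.3.3.1.

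The matter is not trivial for this population. Section 3.1.1(b) lists unintended breach of confidentiality among the risks of the study, and the data sharing plan describes disclosure of substance use or a positive COVID status as potentially very stigmatizing. Prompt IRB review is the outside check that 3.3.3.1 provides. If the IRB hears of a breach only in an annual report, that check comes late.

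**Working it through.** The plan gives no figure to reproduce, so the check sets the provisions side by side.

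**1. Clocks for a breach**

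| Recipient | Section 3.3.3.1 | Table 3.3a, Other AEs | Table 3.3b, Other AEs |
|---|---|---|---|
| IRB | immediate | annual | annual |
| NIDA | immediate | tri-annual | tri-annual |
| Board (PSMB) | not mentioned | tri-annual | tri-annual |

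The IRB and NIDA lines contradict each other. The board line is a gap in the text, not a contradiction.

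**2. Precedence.** Section 3.3.3 introduces the tables as the way in which risk will be defined and measured. Section 3.3.3.2 has the PI submit reports as required. Section 3.3.3.3 points to the table for serious or unexpected events. Section 3.3.3.1 does not mention the reporting rows, and the rows do not mention 3.3.3.1. No sentence ranks them.

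**3. Size of the gap for the named row.** An annual report can follow an event by up to 12 months. If tri-annual means three times a year (an assumption, since the protocol does not define it), the NIDA interval is 12 / 3 = 4 months. Read as once in three years it would be 3 × 12 = 36 months, which exceeds the 2-year study and is implausible.

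**4. Other rows that a breach might meet** (IRB clocks)

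- Unexpected AEs: 5 working days. A breach is named in advance, so it enters here only through a further condition, such as withdrawal of the participant or a deviation from the protocol.
- Unanticipated problems that are not AEs: 5 working days, or immediate if participants are likely to be affected. Both tables class a breach as an AE, so this row applies only if the event is reclassified.
- Protocol violations: 2 weeks, or 5 days if an unanticipated problem results. This needs a departure from approved procedures.

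These routes run from immediate to 2 weeks, but each is conditional, and the tables do not say which row wins.

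**5. Effect on the halt.** In 3.3.3.1 the breach itself triggers the halt; no table clock does. Section 3.3.3.2 has research staff tell the PI of any SAE, AE or unanticipated problem within 48 hours, although its heading speaks of staff events. The person who must halt can therefore act under any row. The halt ends with IRB review, however, and that review cannot begin before the IRB knows. The table clock thus bears on the review and on the length of the halt, not on whether the halt exists.

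**6. SAE clocks to the IRB.** They are 3 working days for staff (Table 3.3a), 5 for testing participants (Table 3.3b) and 5 in section 3.3.3.3, so the largest difference is 5 − 3 = 2 working days. Deaths are at 3 working days in both tables. Every table clock is equal to or shorter than that of 3.3.3.3, so a report that meets the table also meets the text. None of these clocks touches the halt-and-review step.

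**The case against.** The strongest reply is that 3.3.3.1 is the more specific text, comes directly after the tables and is addressed to the PI, who is also the person responsible for informing the IRB and NIDA. A PI who knows the protocol would act on it. In addition, section 3.3.2 provides for quarterly safety review by the monitoring board and a written summary to the IRB after each meeting, so a breach might surface well before a year has passed.

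Part of this stands. The 12-month figure is a bound for one row and not an expected delay, and nothing in the documents shows that staff would rely on the tables in preference to the text. But the protocol nowhere says that the specific text prevails. The quarterly route is also not assured: section 3.3.4 commits the board to meeting only at least once a year besides reading quarterly reports, and the IRB summary is tied to meetings. Neither route amounts to immediate notice.

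A reader might infer that the tables disable the halt, so that data collection would simply continue after a breach. The documents do not support that, because the halt is a separate duty triggered by the breach. A reader might also take the differing SAE clocks as part of the same failure. They are not: the halt applies only to breaches, and the table clocks for SAEs are never looser than the text. Nor do the documents rank breach of confidentiality as the study's main harm; it is one of several risks listed without order.

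**Conclusion.** The contradiction is explicit and should be corrected. For the same named event, notice to the IRB is immediate in 3.3.3.1 and annual in both tables; notice to NIDA is immediate and tri-annual. Followed as written, the table row could delay IRB notice and the review that lifts the halt by up to about 12 months. That bound assumes that the event is reported under the named row alone and that neither a shorter-clock row nor a board summary brings it to the IRB sooner. The 4-month bound for NIDA rests on reading tri-annual as three times a year.

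This is an internal inconsistency in a participant-protection procedure. It does not bear on the primary outcome, the sample size, the assignment of strategies or the analysis. Recruitment is listed as closed in section 2.6, but Healthix data run to 12 months after Phase 2 and data sharing comes later still, so the handling of a breach can matter after enrollment ends. The SAE difference is a minor point of tidiness.

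**What to change.** 1. Take breach of confidentiality out of the Other AEs rows of Tables 3.3a and 3.3b and give it its own row in each, referring to the four steps of section 3.3.3.1. State a clock for the board in that row, since 3.3.3.1 gives none.
2. Add one sentence saying which row takes precedence when an event fits more than one.
3. As housekeeping, reconcile the staff SAE clock in Table 3.3a with those in Table 3.3b and section 3.3.3.3, and the death rows with 3.3.3.3 if deaths count as serious events there. The choice is for the investigators and the IRB.
4. Define tri-annual.

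The cost is a few table entries and a sentence or two in an amendment, with no change to the design, the sample size or data already collected.

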4.1. Brief Summary

We propose research to establish efficacy and sustainability of a community-social network outreach model that partners infectious disease health providers with community based organizations to successfully implement (reach, uptake, delivery and sustainment) COVID-19 point of service, rapid-testing among a highly vulnerable

and often underserved population, those who use opioids and other substances. Two distinct social network recruitment strategies with demonstrated efficacy identifying hidden populations and increasing uptake of HIV testing will be adapted and compared. Guided by the EPIS framework, social cognitive theory, and Andersen's model, this study comprises three phases. Phase 1: Adaptation of outreach recruitment strategies, we will work with our project community advisory board (CAB) to adapt chain-referral and credible messenger strategies for uptake of COVID-19 testing, to finalize recruitment and on-site testing protocols, and to train the CAB in the new protocols and in continuous quality improvement strategies (Aim 1). Phase 2: Strategy Efficacy Trial and Implementation Evaluation, we will compare the two strategies in a cross-over design at two community based organizations (CBOs) with long standing history of serving hard-to-reach populations in their communities. We will examine the impact of each strategy on (i) reach (recruitment of target population), (ii) COVID-19 testing/repeat testing, and (iii) service delivery (i.e. quarantine, medical care and contact tracing) among those who test positive for COVID-19 (exploratory) (Aim 2). Phase 3: Sustainment, CBOs will implement the strategy proven efficacious based on outcomes, and we will examine their sustainment of the program (Aim 2). Implementation evaluation will identify participant-, staff-, and organizational-level factors that influence the feasibility, acceptability, and sustainability of each strategy in these CBOs. (Aim 3). This investigation will provide much needed information to improve health outcomes and to identify effective system-level responses to prevent or arrest the spread of COVID-19 among the social networks of those who use opioids and other substances, a highly vulnerable and often overlooked population. Until the advent of treatment or a vaccine, our ability to contain COVID-19 must rely on widespread identification of (asymptomatic) positive cases, their subsequent quarantine, and contact tracing of those potentially exposed. Therefore testing efforts must be targeted to those highly vulnerable yet unserved populations, including individuals who use opioids and other substances. These individuals may have poor respiratory or pulmonary health due to substance use (e.g. opioids, methamphetamine), which may make them more susceptible to the virus. Also, these individuals are more likely to have been incarcerated, or reside on the street, in shelters, or in crowded accommodation, further placing them at risk for transmission.

4.2. Sample Size Determination

Power calculations assume that we will be able to recruit 500 participants in total (250 recruited in each strategy) for this supplement study over Phases 2a and 2b. We also assume alpha (type I error rate) of 0.05. Our primary outcome of interest is testing occurrence. Based on zip-code level testing data, the average baseline testing in the communities of interest (i.e., northern Manhattan, the Bronx) is 7842.2/100,000. If we assume that one of the methods of recruitment will have a testing rate similar to this baseline average, we will have > 80% power to detect an approximately 8 percentage point difference in testing among the recruitment strategies (7.8% vs. 16.1%) corresponding to an odds ratio of 2.27, a moderate effect size.

4.3. Outcome Measures

Table 5. Outcome Measures

Name	Type	Time Frame	Description
Reach	Primary	Baseline	# of coupons redeemed; (secondary # redeemed/# distributed)
Testing Uptake	Primary	Baseline	Y/N; (secondary # redeemed/# distributed)
Service Delivery (exploratory): Quarantine Medical care Contact tracing	Primary	Baseline	For positive test results only: Y/N self-quarantine Y/N (date 1st apt) Y/N (Agreed to provide names/addresses of network)

Acceptability; Sustainability	Primary	Baseline	Continued recruitment; testing beyond Implementation phase
Feasibility	Primary	Baseline	Recruitment and testing delivery facilitators and barriers;
Fidelity	Primary	Baseline	Recruitment and testing protocol TBD during Phase 1
Organizational Climate, support and functioning, leadership	Secondary	Baseline and post implementation	Innovation/Flexibility; Organization support; Communication, Job satisfaction
Staff Demographics	Secondary	Baseline and post implementation	Gender, age, race/ethnicity, position, job tenure, education
COVID-19 knowledge /attitudes	Secondary	Baseline and post implementation	a) knowledge of symptoms b) subjective effectiveness of safety practices c) subjective safety/unsafe of activities d) vaccination acceptability e) COVID-19 stigma
Perceived potential sustainability of testing program	Secondary	Baseline and post implementation	Program Sustainability Assessment Tool: Political support, Partnerships, Capacity, Evaluation, Communications, (20 items; (.79-.92)

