Recruitment of testing participants. Testing participants will be recruited in one of two ways: chain referral and credible messenger. In the chain referral strategy, an initial set of n=8 “seed” participants are recruitment by staff of eligible clients receiving services at Argus and Alliance (n=16 total seeds). For clinic-based recruitment of “seeds”, participants will be recruited from among those individuals who use opioids and other drugs who are receiving services through Argus or Alliance; services do not need to be substance use related. (Following a brief training, these “seed” participants then recruit additional participants (“peer recruits”) from among their own peer networks of those known to use opioid or other drugs in community settings (peer- recruitment). “Seed” participants are given three unique, numbered coupons, which they can give to people they know (peers) who are also use opioids and other drugs. The coupons will have information, by which peers who are interested in participating in the study can contact the research team to be screened for eligibility. Participants will receive renumeration for each peer recruit who enrolls in the study by redeeming a coupon given to them by that participant. Peer-recruits then repeat the same process with members of their peer network.

The credible messenger strategy involves leveraging the existing infrastructure at both Argus and Alliance, which includes credible messenger programs that are well-established, with considerable influence and impact within the respective communities served by these two agencies. The credible messengers within these programs have been trained to conduct community outreach to target individuals at increased risk for HIV, STIs, HCV and SUD and encourage testing and/or linkage to services. Interested credible messengers (n=4 from each site) will serve as messengers in the current study and will be trained to also include education about COVID-19, ways to reduce risk as well as ways to increase motivation to test for COVID-19 at the respective clinics. Credible messengers will conduct community outreach, targeting those locations and venues where potentially credible participants are located, and will provide education and encourage these individuals to seek testing. The potential participants will be given a coupon which will be redeemed at the clinic when the participant is enrolled in the study after being determined as eligible.

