As testing participants are assessed once and then offered a test immediately thereafter, study retention is not a considerable focus of procedures. Participants recruited by chain-referral will be given a brief survey following their recruitment efforts to document number of attempts, time etc. This brief survey will occur at the visit when the participant comes to the clinic to receive payment for redeemed coupons that s/he distributed to peers; it is anticipated the payment will serve to adequately retain participants for the purpose of completing the brief survey.

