Staff surveys. At the beginning of Phase 2, staff and credible messengers will complete brief surveys. Guided by EPIS, Andersen and SCT, surveys will collect data on theoretically-defined inner-, outer-, and individual-level factors that may influence the implementation of the recruitment strategies and testing. Surveys will capture demographics and professional history, and attitudes and knowledge regarding COVID-19, risk reduction behaviors and testing. Surveys will be available in paper/pencil format as well online via Redcap link; surveys will be administered again at the end of Phase 2 with similar content as well as items on palatability and felt-utility of the different strategies.

Test participant surveys. Following consent and study enrollment, all participants will complete a brief assessment consisting of structured survey examining predisposing and enabling factors (e.g. mental health, substance use, social support/capital), social-cognitive factors (COVID-19 attitudes, knowledge perceived risk, stigma) and structural variables (e.g. housing security; food insecurity) and a social network inventory. A social network inventory will be adapted from previous inventories.^{1,2} The inventory will consist of a set of standard “alter generators,” which are questions asking participants to list names, pseudonyms or initials of individuals within their social networks (“alters”) who fit certain descriptions (e.g. friends, loved ones, drug sharing partners, people who provide material support, etc.). Once alters have been generated and listed in an anonymized fashion, additional questions are asked about each alter to assess their age, frequency of interaction and duration of the relationship. Participants will also be asked about alters’ drug use, as well as previous disclosures of COVID-19 exposure or seropositivity between the participant and his/her alters. RAs will conduct interviews in private rooms at either Argus or Alliance locations. At the end of this survey the participant will receive COVID-19 testing; brief follow-up interviews will occur for those participants included in the chain-referral recruitment strategy when they return to receive compensation for redeemed coupons.

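### Table 5's secondary measure of testing uptake counts no tests, and reach, a clustered count, is left without a model that can take it

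*Combined protocol and SAP*

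**What the plan says.** **Outcome definitions.** Table 5 in section 4.3 defines reach as the number "of coupons redeemed; (secondary # redeemed/# distributed" and testing uptake as "Y/N; (secondary # redeemed/# distributed". Both are typed Primary. Section 4.5.1 instead makes testing occurrence (yes/no) the primary outcome and calls reach, the number of coupons redeemed, an important secondary outcome.

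**Coupon rules (section 2.5).** Chain referral starts from seeds: "participants are recruitment by staff of eligible clients receiving services at Argus and Alliance (n=16 total seeds". Seed "participants are given three unique, numbered coupons, which they can give to people they know (peers". Then: "Peer-recruits then repeat the same process with members of their peer network". Payment depends on redemption: "Participants will receive renumeration for each peer recruit who enrolls in the study by redeeming a coupon given to them by that participant". In the credible messenger strategy, four messengers per site give a coupon to people met in outreach. It is redeemed at the clinic on enrolment, and no number of coupons is stated.

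**Timing of the test.** Section 2.5: "As testing participants are assessed once and then offered a test immediately thereafter". Section 3.1.1(b), on test participant surveys: "At the end of this survey the participant will receive COVID-19 testing".

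**Model.** Section 4.4.1 proposes the logistic form for the primary dichotomous outcome and lists reach in a parenthesis in that sentence. Section 4.5.2 writes out a logistic model for testing uptake and says it will be adapted for secondary outcomes. It gives no distribution, offset, unit of analysis or treatment of referral chains.

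**The concern.** There are three linked problems.

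1. The secondary measure of testing uptake is the coupon ratio already used for reach. Redemption happens at enrolment and the test follows, so the ratio has no test in its numerator or its denominator.

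2. A logistic model for individual participants cannot take a count of redeemed coupons as its outcome. The promise to adapt the model leaves open the main choice, which is how to treat recruits who come in a few chains or through a few messengers. An analysis that treated them as independent would overstate precision.

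3. The ratio of coupons redeemed to coupons distributed is formed under different rules in the two strategies, so a difference may partly reflect those rules.

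What is at stake is the reach comparison. Section 4.4.1 hypothesises that chain referral does better on it, and in Phase 3 the organisations are to continue with the strategy judged efficacious on the outcomes.

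**Working it through.** **The plan's own power figure.** Section 4.2 gives more than 80% power for 7.8% against 16.1% with 250 per strategy. The mean rate is 0.1195. Pooled SE = √(2 × 0.1195 × 0.8805 / 250) = 0.0290. Unpooled SE = √((0.078 × 0.922 + 0.161 × 0.839) / 250) = 0.0288. Power = Φ((0.083 − 1.96 × 0.0290) / 0.0288) = 81.8% (two-sided 5%). Odds ratio = (0.161/0.839) / (0.078/0.922) = 2.27. Both figures reproduce, but they concern yes/no testing only. No power figure is given for reach.

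**Testing uptake cell.** The order of events is coupon handed over, coupon redeemed at enrolment, survey, test. A ratio that stops at redemption cannot measure testing.

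**Reach as a clustered count.** Inputs from section 2.5: 16 seeds, three coupons per participant, 8 messengers. Assumptions: 7 waves, each coupon redeemed independently with probability p, and messenger counts that are Poisson with the same expected total as the chains. Expected chain recruits = 16 × Σ(3p)^k for k = 1 to 7. Two tests at two-sided 5% were simulated on the log rate ratio: a plain Poisson test, and a t test using variance between chains and between messengers (Satterthwaite degrees of freedom).

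| p | Expected recruits | Plain Poisson, false positives | Cluster-based t |
|---|---|---|---|
| 10% | 7 | about 6% | about 3% |
| 20% | 23 | about 22% | about 7% |
| 30% | 75 | about 41% | about 7% |
| 40% | 248 | about 55% | about 5% |
| 50% | 772 | about 65% | about 5% |

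Under these assumptions, p = 40% is the row close to the target of 250 per strategy. There the chain total has mean 248, SD about 72 and variance/mean about 21, where Poisson assumes 1. With 5 waves the Poisson figure at 40% falls to about 40%. With a messenger coefficient of variation (CV) of 0.5 and 7 waves it rises to about 61%. At p = 10% the result depends on the form of the test: a score version gives about 9%. At p = 25% the cluster-based test gives about 8%.

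**Precision of reach at p = 40%.** The 95% limits are the estimate multiplied and divided by exp(1.96 × √(72.1²/247.8² + CV²/8 + 1/250)). This is 1.79 for messenger CV 0, 1.97 for 0.5 and 2.47 for 1. Poisson for both strategies gives exp(1.96 × √(2/250)) = 1.19.

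**Coupon ratio.** Suppose 250 chain participants include the 16 seeds, so that 234 coupons are redeemed.
- If distributed means issued and everyone is issued three: 234/750 = 31.2%.
- If 10% or 20% are issued none: 234/675 = 34.7% or 234/600 = 39.0%.
- Messengers with 250 redeemed: 250/500 = 50%, or 250/2,500 = 10%. The numbers handed out are illustrative, since the plan states none.

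**The case against.** **The coupon ratio.** A reader might infer that the chain ratio can never exceed one third while the messenger ratio has no ceiling. The documents do not support this as a general statement. Section 2.5 uses distributed for coupons a chain participant passes to peers, which matches a messenger handing one to a contact. Section 3.1.1(a) also bars chain recruits who test positive from recruiting until a negative nucleic acid test, so not everyone need be issued three. The ceiling arises only if distributed means issued and every participant is issued three. What remains is that chain participants hold at most three coupons and are paid per redemption, while no coupon number is stated for messengers.

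**Time base.** A reader might infer that a raw count is meaningless, or is fixed in advance at 250 per strategy. Section 3.1.1(a) plans a 4-month roll-out before the cross-over within an 8-month period, so planned exposure is nominally equal, and 250 is an aim rather than a stated cap. A rate per site-week handles unequal actual exposure; its absence is not a fatal flaw.

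**Poisson.** The plan never proposes a plain Poisson test, so a false-positive rate of 55% cannot be attributed to it. The figure shows what one natural adaptation would do in one scenario. The objection stands as a limit on the claim, but leaves the gap in the plan.

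**Uptake.** The yes/no measure is correct, and the faulty cell may be a slip. Enrolled people are tested at the end of the survey, so tests per site-week would nearly duplicate the reach rate. A ratio with coupons handed out as denominator keeps people who never enrolled, which is a reason to replace the measure rather than only delete it.

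**Conclusion.** The point holds in three parts of unequal strength.

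1. The secondary testing uptake measure in Table 5 counts no tests and is wrong as written. The main yes/no measure and its power calculation are unaffected.

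2. The model for reach is wrong in section 4.4.1, which places a count under an individual-level logistic form, and unspecified in section 4.5.2. A plain Poisson adaptation would have a false-positive rate of about 6% to 65% at equal expected reach, and about 55% at 40% redemption. This rests on 7 waves, independent redemption at 10% to 50% per coupon and no extra messenger variation.

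3. A comparison of redeemed/distributed between strategies is hard to interpret. This part is a matter of definition and rests on the coupon rules alone; no fixed bias can be computed from the documents.

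A reader might also think that the 16 staff-recruited seeds distort uptake. That is not part of this defect, and a sensitivity analysis without them is optional.

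**What to change.** 1. **Testing uptake row.** Replace the secondary measure with one that counts tests: coupon-recruited persons tested per coupon handed out, within each strategy, or per site-week. Otherwise delete it.

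2. **Reach.** Compare coupon-recruited eligible enrollees per site-week over each roll-out. Use a log-link count model with strategy, site and period, fitted to counts per chain (traced to the seed) and per messenger, zeros included. With 8 chains but 4 messengers per site, the offset should be site-weeks divided by that number, so that the rate ratio is per site-week. Take the uncertainty from variation between chains and between messengers. Where messenger identifiers were not recorded, say so and report the comparison as descriptive.

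3. **Distributed.** State that it means handed to a person, name the data source, and report redeemed/distributed descriptively within each strategy.

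**Cost.** Most of this is wording in Table 5 and sections 4.4.1 and 4.5. Chain coupons are numbered, and section 3.3.3.1 has coupons recorded electronically. Messenger coupons are not described as numbered. Section 2.6 gives the status as not recruiting and Table 1 tabulates 486 participants, so a missing messenger identifier may not be recoverable.

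**Downsides.** The limits for reach widen to a factor of about 1.8 to 2.5, against 1.2 under Poisson (40% redemption, 7 waves). The cluster-based t test had an error rate of about 3% to 8% in these scenarios, not a uniform 5%, and the site and period terms were not simulated. Four site-periods cannot cover site-by-period variation.
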